#### 9. SAFETY AND TOLERABILITY

Appendix A provides a list of data displays. Sample data displays are included in a separate document.

#### 9.1. General Considerations

All safety analyses will be conducted using the FAS and summarized by treatment group.

#### 9.2. Adverse Events

#### 9.2.1. Adverse Event Definitions

A TEAE is either an AE reported for the first time or worsening of a pre-existing event after first dose of itacitinib until 30 days after the last dose of itacitinib. Analysis of AEs will be limited to TEAEs, but data listings will include all AEs regardless of their timing in relation to the administration of itacitinib.

Adverse events will be tabulated by MedDRA PT and SOC. Severity of AEs will be described and graded using the NCI CTCAE v5.0 (2017). The CTCAE reporting guidelines and grading details are available on the Cancer Therapy Evaluation Program website.

A grading (severity) scale is provided for each AE term. If the toxicity is not included in the CTCAE v5.0 criteria, then it will be rated on a scale of 1 to 4 as follows: 1 = mild, 2 = moderate, 3 = severe, and 4 = life-threatening. All toxicities will be graded based on the worst level reached, not the level they may have reached if they had not been treated. When the intensity of an AE changes over time for a reporting period (eg, between visits), then each change in intensity will be reported as an AE until the event resolves.

The subset of AEs considered by the investigator to be related to itacitinib will be considered to be treatment-related AEs. If the investigator does not specify the relationship of the AE to itacitinib, then the AE will be considered to be treatment-related. The incidence of AEs and treatment-related AEs will be tabulated. Serious AEs will also be tabulated.

Any missing onset date, causality, or severity must be queried for resolution. Unsolved missing values will be handled according to the following rules:

- An unsolved missing causality will be considered treatment-related.
- An unsolved missing severity will be identified as an unknown severity.

For purposes of analysis, all AEs will be considered TEAEs unless the AE can unequivocally be defined as not treatment-emergent.

#### 9.2.2. Adverse Event Summaries

An overall summary of AEs by treatment group will include:

- Number (%) of participants reporting any TEAEs
- Number (%) of participants reporting any serious TEAEs
- Number (%) of participants reporting any Grade 3 or higher TEAEs
- Number (%) of participants reporting any TEAEs related to itacitinib

- Number (%) of participants who temporarily interrupted itacitinib because of TEAEs
- Number (%) of participants with itacitinib dose reduction because of TEAEs
- Number (%) of participants who permanently discontinued itacitinib because of TEAEs
- Number (%) of participants who had a fatal TEAE

The following summaries will be produced by MedDRA term:

- Summary of TEAEs by MedDRA SOC and PT
- Summary of TEAEs by MedDRA PT in decreasing order of frequency
- Summary of TEAEs by MedDRA SOC, PT, and maximum severity
- Summary of Grade 3 or higher TEAEs by MedDRA SOC and PT
- Summary of Grade 3 or higher TEAEs by MedDRA PT in decreasing order of frequency
- Summary of serious TEAEs by MedDRA SOC and PT
- Summary of serious TEAEs by MedDRA PT in decreasing order of frequency
- Summary of itacitinib treatment-related TEAEs by MedDRA SOC and PT
- Summary of itacitinib treatment-related TEAEs by MedDRA PT in decreasing order of frequency
- Summary of itacitinib treatment-related serious TEAEs by MedDRA SOC and PT
- Summary of TEAEs with a fatal outcome by MedDRA SOC and PT
- Summary of TEAEs leading to discontinuation of itacitinib by MedDRA SOC and PT
- Summary of TEAEs leading to itacitinib dose reduction by MedDRA SOC and PT
- Summary of TEAEs leading to itacitinib dose interruption by MedDRA SOC and PT

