Number of Participants	Phase 1: Approximately 24 participants, to be treated at 3 different dose levels (n = 8 each) Phase 2: Up to approximately 55 participants
Study Design	Phase 1: Randomized, open-label Phase 2: Single-arm, open-label
Estimated Duration of Study	Up to 30 days for screening, continuous treatment as long as participants are receiving benefit and have not met any criteria for treatment discontinuation, 30 days for safety follow-up, and participants enrolled in Phase 2 will be followed for long-term survival and retransplantation status. Study participation, including survival follow-up, is expected to average approximately 24 months per participant.
Study Steering Committee	A steering committee comprised of the coordinating PI and select sponsor personnel will review the cumulative Phase 1 data and provide a recommendation for the Phase 2 dose.

Figure 1: Study Design Schema

^a Not inclusive; see Section 4 for complete eligibility criteria.

Adherence to the study design requirements, including those specified in the SoA (see [Table 2](#)), is essential and required for study conduct.

Table 2: Schedule of Activities

Visit Day (Range)	Screening	Treatment							EOT	Safety Follow-Up (30 d + 7 d)	Notes
	Days -30 to -1	Baseline (Day 1)	Week 1 (± 1 d)	Week 2 (± 3 d)	Weeks 4 and 8 (± 7 d)	Week 12 (± 7 d)	Week 16 and Q4W thereafter (± 14 d)				
Administrative procedures											
Informed consent	X										See Section 8.1.1 for details.
Register visit in IRT	X	X			X	X	X	X			See Section 8.1.3 for details.
Inclusion/exclusion criteria	X	X									See Section 5 for details.
Demography	X										See Section 8.1.5 for details.
Relevant medical and transplant history	X										See Sections 8.1.5 and 8.1.6 for details.
Prior/concomitant medications	X	X	X	X	X	X	X	X			See Section 6.3 for details.
Study drug dispensing and accountability		X			X	X	X	X			See Section 6.4 for details.
Dispense reminder card		X	X	X	X	X	X	X			See Section 8.1.4 for details.
Safety assessments											
AE assessment	X	X	X	X	X	X	X	X			See Section 8.3.1 for details.
Comprehensive physical	X										See Section 8.3.2 for details.
Targeted physical exam		X	X	X	X	X	X	X			See Section 8.3.2 for details.
Vital signs/weight	X*	X	X	X	X*	X*	X*	X*	X		See Section 8.3.3 for details. * Weight performed.
12-Lead ECG	X	As clinically indicated						X			See Section 8.3.4 for details.
Disease assessments											
Spirometry (FEV ₁ and FVC)	X	X	X	X	X	X	X	X			See Section 8.2.1 for details.

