4. STUDY DESIGN

4.1. Overall Design

This Phase 1/2 study will evaluate the safety, efficacy, PK, and PD of itacitinib in participants with post-lung transplant BOS.

Phase 1 is a dose selection run-in that will employ a randomized, open-label, parallel-cohort design to assess the safety, tolerability, PK, and PD and to determine the RP2D of itacitinib in participants with post-lung transplant BOS. A total of 24 participants with Grade 1, 2, or 3 BOS will be assigned to receive 1 of 3 itacitinib dose levels ($n = 8$ each); see [Table 9](#) for additional details regarding itacitinib dose levels. Each Phase 1 dose level will enroll a maximum of 2 participants with Grade 3 BOS. Participants will be randomized to 1 of 3 dose levels using an IRT system. Upon completion of Phase 1 enrollment, the RP2D will be selected on the basis of AE, laboratory, PK, and PD observations through the Week 12 visit. Additionally, an efficacy analysis will be performed to determine the FEV_1 response rate for all participants treated for ≥ 12 weeks. The study will proceed to Phase 2 if ≥ 1 responses (defined as $\geq 10\%$ absolute increase in FEV_1 compared to baseline, confirmed by 2 consecutive spirometric assessments ≥ 1 week apart) are observed at the dose level selected as the RP2D.

Phase 2 will employ a single-arm, open-label design to evaluate the efficacy and further characterize the safety of itacitinib at the RP2D.

Itacitinib treatment in Phase 1 and Phase 2 will continue until progression of BOS (defined as a $\geq 10\%$ absolute decrease from baseline in FEV_1 , confirmed by 2 consecutive spirometric assessments ≥ 3 weeks apart), unacceptable toxicity, loss of clinical benefit, or withdrawal of consent. Additional criteria for treatment discontinuation are detailed in Section [7.1](#).

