6. STUDY TREATMENT

6.1. Study Treatment Administered

Information regarding study drug and administration is provided in [Table 8](#).

Once eligibility is confirmed, participants enrolling into Phase 1 will be randomized to an assigned dose level (see [Table 9](#)), will begin the treatment period on Day 1, and will continue on study treatment until discontinuation criteria are met.

Participants enrolling into Phase 2, upon confirmation of eligibility, will begin treatment at the RP2D determined in Phase 1.

Table 8: Study Treatment Information

Study treatment name:	Itacitinib	
Dosage formulation:	Sustained release tablet	
Unit dose strength:	100 mg	
Route of administration:	Oral	
Administration instructions:	
During Phase 1, participants will be randomized to 1 of 3 dose levels, as outlined in Table 9. Itacitinib administration will continue daily at the assigned dose until treatment discontinuation.
 
Phase 2 participants will be administered itacitinib at the RP2D, which will be selected based on the criteria outlined in Section 6.1.1.
 
Itacitinib may be taken without regard to food except on PK days.
 
Missed doses must be taken within 8 hours after the scheduled time of administration; however, if this window is not met, the missed dose will be documented as not taken and the next scheduled dose will be taken as scheduled.
	
Packaging and labeling:	
Itacitinib will be provided in 35-count bottles.
 
Investigational product labels will be in the local language and will be labeled as required per country requirement.
	
Storage:	Ambient 15°C-30°C (59°F-86°F)	

Table 9: Itacitinib Dose Levels

Itacitinib Dose Level	Starting Dose		First Dose Level Reduction		Second Dose Level Reduction	
	A: No CYP3A	B: With CYP3A	A: No CYP3A	B: With CYP3A	A: No CYP3A	B: With CYP3A
Dose Level 1	300 mg BID	200 mg BID	200 mg BID	100 mg BID	100 mg BID	100 mg QD
Dose Level 2	400 mg QD	300 mg QD	300 mg QD	200 mg QD	200 mg QD	100 mg QD
Dose Level 3	600 mg QD	400 mg QD	400 mg QD	300 mg QD	300 mg QD	200 mg QD

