10.4.3.1. Adverse Events

A TEAE is any AE either reported for the first time or worsening of a pre-existing event after first dose of study drug until 30 days after the last dose of study drug. Analysis of AEs will be limited to TEAEs, but data listings will include all AEs regardless of their timing to study drug administration. Adverse events will be tabulated by the MedDRA preferred term and system organ class. Severity of AEs will be based on the NCI CTCAE v5.0.

The subset of AEs considered by the investigator to have a relationship to study drug will be considered to be treatment-related AEs. If the investigator does not specify the relationship of the AE to study drug, the AE will be considered treatment-related. The incidence of AEs and treatment-related AEs will be tabulated.

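### By-dose adverse event tables cover an open-ended treatment period with no Week 12 cut, so any difference in time on drug between dose levels enters the Phase 1 safety percentages

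*SAP*

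**What the plan says.** The Phase 1 primary objective is to identify a dose. Frequency, severity and duration of AEs are the first-listed part of its endpoint (Protocol Table 6, SAP Table 1).

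- **Dose-selection window.** Protocol 4.1: "the RP2D will be selected on the basis of AE, laboratory, PK, and PD observations through the Week 12 visit". Protocol 6.1.1 and SAP 3 set the same window.
- **Treatment duration.** Protocol 4.1: "Itacitinib treatment in Phase 1 and Phase 2 will continue until progression of BOS", or until unacceptable toxicity, loss of clinical benefit or withdrawal of consent. Protocol 6.1 says that participants "will continue on study treatment until discontinuation criteria are met". The protocol summary describes "continuous treatment as long as participants are receiving benefit and have not met any criteria for treatment discontinuation".
- **AE counting window.** SAP 9.2.1 counts a TEAE "after first dose of itacitinib until 30 days after the last dose of itacitinib". Protocol 10.4.3.1 matches: "after first dose of study drug until 30 days after the last dose of study drug".
- **AE measure.** SAP 9.1 uses the full analysis set by treatment group. The overall summary in SAP 9.2.2 consists of lines such as "Number (%) of participants reporting any Grade 3 or higher TEAEs". The AE tables in Appendix A (within 3.2.1 to 3.2.15) follow this pattern. None is cut at Week 12, none uses patient-time, and none gives time to first event.
- **Exposure.** Treatment duration is defined in SAP 6.4 and reported separately in Table 3.1.1.

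**The concern.** The plan names one AE window for judging the doses and tabulates another. Under an open-ended window, a participant treated for a year has far longer to record an event than one who stops after a few weeks. The stopping rules (toxicity, BOS progression, loss of benefit) are ones that dose could plausibly influence. A dose level whose participants stop early would have less time to collect events and could look safer than it is. A level whose participants benefit and stay on could look more toxic.

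The full analysis set also keeps everyone who took one dose. Phase 1 participants replaced under Protocol 5.5 for taking 75% or less of planned doses up to Week 12 therefore stay in the denominators, some of them with short windows.

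FEV₁ is summarized by visit (SAP 7.3, Table 2.2.1), so a reader can compare the doses at Week 12 on lung function. No table allows the same for adverse events.

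**Working it through.** **The plan's own figure.** The only number behind these percentages is the Phase 1 size: 3 dose levels × 8 = 24, as stated in Protocol 10.1.1 and SAP 3.3. It is a descriptive size with no power calculation. The documents give no AE rate and no time on drug by dose level, so what follows illustrates the mechanism and does not estimate what happened.

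**Model (assumed).** Every dose level has the same constant hazard *h* of a first event. With *T* years on drug and the 30-day tail, the expected crude percentage is

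P = 1 − exp[−*h* × (*T* + 30/365.25)].

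Example: *h* = 0.5, 12 weeks on drug: *T* = 84/365.25 = 0.230, window 0.230 + 0.082 = 0.312 years, P = 1 − exp(−0.156) = 14.4%.

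| Time on drug | Window (years) | *h* = 0.5 | *h* = 1.0 |
|---|---|---|---|
| 12 weeks | 0.312 | 14.4% | 26.8% |
| 6 months | 0.582 | 25.3% | 44.1% |
| 1 year | 1.082 | 41.8% | 66.1% |
| 2 years | 2.082 | 64.7% | 87.5% |

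Ratios that arise with no true difference in toxicity:

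- 6 months versus 1 year: 41.8/25.3 = 1.7 and 66.1/44.1 = 1.5.
- 12 weeks versus 1 year: 41.8/14.4 = 2.9 and 66.1/26.8 = 2.5.
- 12 weeks versus 2 years (extreme): 64.7/14.4 = 4.5 and 87.5/26.8 = 3.3.

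**What this does with 8 per level.** Take a 12-week risk *p*, so that the weekly hazard is −ln(1 − *p*)/12. For *p* = 20% this is 97 first events per 100 patient-years. One level is treated for 24 weeks and another for 52, each with the 30-day tail. Summing the two independent binomials (n = 8 each) gives the chance that the longer-treated level shows at least 3 more affected participants:

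| 12-week risk | Expected % (24 weeks) | Expected % (52 weeks) | Chance of ≥ 3 more, full window | Chance of ≥ 3 more, both cut at 12 weeks |
|---|---|---|---|---|
| 10% | 22.0 | 39.0 | 27% | 1.8% |
| 20% | 40.9 | 64.9 | 39% | 5.6% |
| 30% | 56.9 | 81.2 | 38% | 8.4% |

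**Reach of a Week 12 cut.** Anyone whose last dose falls on or after about Day 54 (84 − 30) has the whole 12 weeks at risk. Only earlier stoppers keep a shorter window, so the cut removes most of the artefact but not all of it.

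**Precision.** Small numbers limit any version of the table: 2 of 8 has an exact 95% CI of 3.2% to 65.1%.

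**The case against.** The strongest reply is that no dose choice depends on these tables, and that is correct. The dose recommendation belonged to a steering committee working under its own charter (Protocol 6.1.1), using an informal analysis (Protocol 10.5, SAP 10). Phase 1 data were analyzed in September 2021, and the sponsor did not open Phase 2, for reasons unrelated to benefit/risk (Protocol 2.3). The original SAP is dated 12 APR 2023. A reader might infer that distorted tables drove, or will drive, the dose choice; the documents do not support that.

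Other parts of the reply also stand:

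- A reader might infer that the early AE data go unreported. They do not: Listings 2.7.1 to 2.7.6 cover the events, and SAP 9.2.1 lists all AEs regardless of timing. What is missing is a Week 12 tabulation.
- Table 3.1.1 shows exposure, although a separate duration summary does not let a reader recover Week 12 incidence.
- Protocol 10.1.1 plans no formal comparison between dose levels. The issue is therefore one of interpretation and not of a wrong test. Still, tables split by dose level invite comparison, and description is all that Phase 1 offers.
- Time on drug may not differ by dose. The levels are randomized and share the same stopping rules, and no durations are reported. A dependence on dose is plausible but not shown.

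It is also tempting to quote distortions of up to nearly sixfold (63.2/10.9 = 5.8 at *h* = 0.5, 12 weeks versus 2 years). That figure omits the 30-day tail and sets one whole dose level at 12 weeks against another at 2 years.

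**Conclusion.** The point holds as a reporting gap. The planned AE tables do not use the Week 12 window that the plan sets for judging the doses, and their open-ended window mixes toxicity with time on drug whenever exposure differs between dose levels.

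The size depends on facts that the documents do not give. Under an equal constant hazard of 0.5 to 1.0 per patient-year, moderate imbalance (6 months versus 1 year) inflates one level's percentage about 1.5- to 1.7-fold, and larger imbalance (12 weeks versus 1 year) about 2.5- to 2.9-fold. If exposure turns out similar across levels, the effect largely vanishes. The direction cannot be known in advance.

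The consequence is confined to the final by-dose account of the Phase 1 primary safety endpoint. The change is worth making because it is cheap and matches the plan's own window.

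**What to change.** In SAP 9.2.2 and Appendix A:

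1. Repeat Tables 3.2.1, 3.2.2, 3.2.5 and 3.2.7 by dose level, restricted to TEAEs with onset through the Week 12 visit, or through 30 days after last dose if that is earlier. Identify these as the AE summary for the Phase 1 dose objective. If the data are already locked, label them supplementary.
2. Keep the crude full-period tables, with a footnote giving median exposure per dose level from Table 3.1.1.
3. Optionally add first-event incidence per 100 patient-years at risk, with exact Poisson 95% CIs, for Grade 3 or higher and serious TEAEs. Label it descriptive, and state that it assumes a roughly constant hazard and does not remove informative stopping.

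No new data are needed: AE onset dates and treatment duration are already collected, and SAP 9.2.1 requires missing onset dates to be queried. The cost is SAP wording, four repeat tables, one or two more if item 3 is taken up, and wide intervals with about 8 participants per dose level.

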# 9.2.3. Clinically Notable Treatment-Emergent Adverse Events Based on Customized MedDRA Queries

The following categories of clinically notable events will be summarized based on customized MedDRA queries (see Appendix B):

- Anemia
- Neutropenia
- Thrombocytopenia
- QT prolongation
- Hyperlipidemia
- EBV infection
- CMV infection

Within each category, the number and percentage of participants with at least 1 TEAE occurring during the treatment phase tabulated by MedDRA PT will be summarized. Summaries of clinically notable TEAEs based on customized MedDRA queries will be provided by treatment group, category, PT, and the highest grade or outcome as follows:

- Overall summary of clinically notable TEAEs in the treatment phase based on customized MedDRA queries.
- Number (%) of participants with clinically notable TEAEs in the treatment phase based on customized MedDRA queries by PT and outcome.
- Number (%) of participants with clinically notable TEAEs in the treatment phase based on customized MedDRA queries by PT and highest grade.

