8.3. Safety Assessments

8.3.1. Adverse Events

Adverse events will be monitored from the time the participant signs the ICF until at least 30 days after the last dose of study drug. Adverse events that begin or worsen after informed consent should be recorded on the Adverse Events Form in the eCRF regardless of the assumption of a causal relationship with study drug. Conditions that were already present at the time of informed consent should be recorded on the Medical History Form in the eCRF.

Adverse events (including laboratory abnormalities that constitute AEs) should be described using a diagnosis whenever possible rather than by individual underlying signs and symptoms.

Adverse events will be reported by the participant (or, when appropriate, by a caregiver, surrogate, or the participant's legally authorized representative). The investigator and any qualified designees are responsible for detecting, documenting, and recording events that meet the definition of an AE or SAE and remain responsible for following-up on AEs that are serious, considered related to the study treatment/procedures, or that caused the participant to discontinue study treatment. Care will be taken not to introduce bias when detecting AEs and/or SAEs. Open-ended and nonleading verbal questioning of the participant, such as "How are you feeling?" is the preferred method to inquire about AE occurrences. Adverse events may also be detected when they are volunteered by the participant during the screening process or between visits, or through physical examinations, laboratory tests, or other assessments. The definition, reporting, and recording requirements for AEs are described in [Section 9](#).

All SAEs will be recorded and reported to the sponsor or designee within 24 hours. The investigator will submit any updated SAE data to the sponsor within 24 hours of it being available.

After the initial AE/SAE report, the investigator is required to proactively follow each participant at subsequent visits/contacts. All SAEs will be followed until resolution, stabilization, the event is otherwise explained, or the participant is lost to follow-up (as defined in Section 7.3).

The severity of AEs will be determined per CTCAE v5.0.

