Rationale for change: As of the date of Amendment 4, 5 study participants have had observed CMV viremia/reactivation, which required treatment with antiviral agents. The requirement for serial CMV testing during study treatment was added to ensure that all cases of CMV reactivation are identified and appropriately treated.

2. **Appendix D, COVID-19 Pandemic Mitigation Strategies and Instructions**

Description of change: Added appendix to provide guidance for protocol considerations during the COVID-19 pandemic.

Rationale for change: Guidance due to pandemic.

3. **Incorporation of administrative changes.** Other minor, administrative changes have been incorporated and are noted in the redline version of the amendment.

Amendment 3 (11 AUG 2020)

Overall Rationale for the Amendment: The primary purpose of this amendment is to update the schedule of assessments to require monitoring of maintenance immunosuppressive agents (eg, CNIs) and to require that participants are on stable doses of strong CYP3A inhibitors prior for 4 weeks before starting study drug.

1. Section 1, Protocol Summary (Table 3, Schedule of Laboratory Assessments); Section 5.2, Exclusion Criteria (Criterion 8); Section 8.3.5, Laboratory Assessments

Description of change: A requirement was added to monitor levels of maintenance immunosuppressive medications at all visits through Week 8.

Rationale for change: In this study, elevated levels of tacrolimus have been observed in 3 of 3 participants who have received doses of itacitinib > 200 mg/day. No causal relationship has been established. Immunosuppressive medication level monitoring has been added as an additional safety measure.

2. Section 1, Protocol Summary (Table 3, Schedule of Laboratory Assessments)

Description of change: Blood chemistry sampling was added to the Schedule of Laboratory Assessments at Weeks 1 and 2.

Rationale for change: To monitor blood chemistry parameters at Weeks 1 and 2.

3. Section 2.2, Study Rationale

Description of change: Added additional background data regarding REACH2 study evaluating ruxolitinib in steroid acute steroid-refractory GVHD.

Rationale for change: To provide additional scientific rationale for this study.

4. Section 5.1, Inclusion Criteria (Criterion 9); Section 6.1, Study Treatments Administered; Section 6.3.3, Prohibited Medications

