# APPENDIX B. CLINICALLY NOTABLE EVENTS BASED ON CUSTOMIZED MEDDRA QUERIES

This appendix provides the categories of clinically notable events based on customized MedDRA queries.

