### **Clinically Notable Hematological Events**

Category	Preferred Term
Anemia	Anaemia macrocytic
Anemia	Aplasia pure red cell
Anemia	Aplastic anaemia
Anemia	Erythroblast count decreased
Anemia	Erythropenia
Anemia	Hypoplastic anaemia
Anemia	Microcytic anaemia
Anemia	Red blood cell count decreased
Anemia	Anaemia
Anemia	Haematocrit decreased
Anemia	Haemoglobin decreased
Anemia	Leukoerythroblastic anaemia
Neutropenia	Agranulocytosis
Neutropenia	Band neutrophil count decreased
Neutropenia	Febrile neutropenia
Neutropenia	Granulocyte count decreased
Neutropenia	Granulocytopenia
Neutropenia	Neutropenia
Neutropenia	Neutropenic infection
Neutropenia	Neutropenic sepsis
Neutropenia	Neutrophil count decreased
Thrombocytopenia	Acquired amegakaryocytic thrombocytopenia
Thrombocytopenia	Platelet count decreased
Thrombocytopenia	Thrombocytopenia
Thrombocytopenia	Plateletcrit decreased

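### The Appendix B term lists behind SAP 9.2.3 hold no multi-lineage cytopenia term and no CMV or EBV reactivation term, so an event coded that way drops out of its clinically notable category

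*SAP*

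**What the plan says.** SAP 9.2.3 names seven categories: anemia, neutropenia, thrombocytopenia, QT prolongation, hyperlipidemia, EBV infection and CMV infection. It ties them to an appendix: "The following categories of clinically notable events will be summarized based on customized MedDRA queries (see Appendix B"). The counting rule, quoted up to its final verb, reads: "Within each category, the number and percentage of participants with at least 1 TEAE occurring during the treatment phase tabulated by MedDRA PT will be" (…). Further summaries by outcome and by highest grade are promised by treatment group.

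Appendix B opens: "This appendix provides the categories of clinically notable events based on customized MedDRA queries". What follows is a set of category and preferred-term pairs. Neither section says that the lists are examples or gives a rule for adding terms.

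On recording, Protocol 8.3.1 says that adverse events "should be described using a diagnosis whenever possible rather than by individual underlying signs and symptoms". On events already seen, the Amendment 4 rationale in Protocol Appendix E reports that "5 study participants have had observed CMV viremia/reactivation, which required treatment with antiviral agents".

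**The concern.** With a closed list, a participant enters a category only if the coded term is on that category's list. A fall in several blood lines recorded as one diagnosis, or a CMV event coded as a reactivation, matches nothing on the lists as printed.

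These are named safety interests. Protocol 2.1.2 discusses the risk of cytopenias, and Protocol 2.2 says that treatment-related thrombocytopenia drove the dose carried forward in acute GVHD. The summary of ruxolitinib studies in Protocol 2.2 reports both cytopenias and CMV reactivation under those names. Phase 1 is meant to identify a dose, partly from adverse event frequency and severity. With eight participants per dose level, one participant missing from a category changes its incidence visibly.

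The lists also look intended to be broad: they include remote terms such as congenital CMV infection, X-linked lymphoproliferative syndrome and plateletcrit decreased. No reason is given for leaving out the broader cytopenia terms or the reactivation terms.

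**Working it through.** The plan states no figure here to reproduce. The check is of list content, followed by simple proportions.

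**Step 1. Content of the lists (SAP Appendix B).**

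| Category | Terms listed | Multi-lineage cytopenia term | Reactivation term |
|---|---|---|---|
| Anemia | 12 | none | n/a |
| Neutropenia | 9 | none | n/a |
| Thrombocytopenia | 4 | none | n/a |
| CMV | 27 | n/a | none |
| EBV | 12 | n/a | none |

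Pancytopenia, bicytopenia, cytopenia on its own and bone marrow terms do not occur. The lists are made up of entries such as "Leukoerythroblastic anaemia", "Band neutrophil count decreased" and "Acquired amegakaryocytic thrombocytopenia". Aplastic and hypoplastic anaemia are the nearest to a marrow-failure term. They are filed under anemia only and would not catch an event coded as pancytopenia. The QT and hyperlipidemia lists would not catch any of these events either.

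**Step 2. What is already caught.** The CMV list includes viraemia, infection, syndrome, disseminated infection, a positive test and many organ-specific terms. Only coding to a reactivation term falls outside it.

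**Step 3. Size of one missed participant.** Planned Phase 1 size is 24, with 8 per dose level (SAP 5.2).

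- Within a dose level: 1/8 = 12.5 percentage points.
- Across Phase 1: 1/24 = 4.2 percentage points.
- One multi-lineage event in a participant with no listed single-lineage term could remove that participant from up to three hematology categories.

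**Step 4. Range for CMV.** Assume that all five known cases are treatment-emergent, that 24 participants were treated, and that k of the five were coded to a reactivation term with no other listed CMV term. The category then shows (5 − k)/24:

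| k | Shown in category |
|---|---|
| 0 | 5/24 = 20.8% |
| 1 | 4/24 = 16.7% |
| 2 | 3/24 = 12.5% |
| 3 | 2/24 = 8.3% |
| 4 | 1/24 = 4.2% |
| 5 | 0/24 = 0% |

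The documents do not give k, and k = 0 is possible.

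**Step 5. Whether the summaries are still planned.** SAP 9.2.3 says that they will be provided. The adverse event tables in Appendix A end at 3.2.15, and neither its tables nor its listings include a clinically notable display. SAP 11.2.1 says that Appendix A was cut back after early termination. Where the quality-of-life analyses were dropped, SAP 7.1 says so; 9.2.3 carries no such statement.

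**The case against.** The strongest reply is that nothing is lost. An event coded as pancytopenia or CMV reactivation would still appear in the planned tables by system organ class and preferred term. Where applicable it would also appear in the maximum-severity, Grade 3 or higher, serious, treatment-related, discontinuation, reduction and interruption tables, and in listings 2.7.1 to 2.7.6. Hematology values are listed in 2.8.1. With about 24 participants, one such event is easy to see. All of this stands, and it limits the point to the category counts.

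Second, the loss depends on coding. The documents do not say that the MedDRA version in use has separate preferred terms for these concepts, or that any event was coded to them. No pancytopenia is reported in this study. This stands too, and makes the point conditional.

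Third, a reader might infer from Protocol 8.3.1 that sites must merge a three-line fall into one pancytopenia event. The text does not go that far. It contrasts a diagnosis with signs and symptoms, and the parallel instruction in Protocol 9.1 uses single-lineage diagnoses (anemia, thrombocytopenia) as its examples. Both say whenever possible. The earlier itacitinib safety table in Protocol 2.2 reports separate blood-line terms with no pancytopenia row. Merging is allowed, but not required.

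Fourth, the category tables may have been dropped, in which case no incidence exists to be understated. Appendix A supports that reading and 9.2.3 contradicts it. What remains is a list that does not cover wording the protocol itself uses, for summaries the SAP text still promises.

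**Conclusion.** The gap in the lists is a fact of the text; its effect is conditional. A category is understated only if an event is coded to an unlisted term, the participant has no other listed term in that category, and the 9.2.3 summaries are produced. The size is then 12.5 points per participant in a dose level of 8, or 4.2 points of 24. For CMV it is 0 to 5 of the five cases known at Amendment 4. The denominators are the planned ones; the treated numbers may differ.

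Two stronger readings are not supported. A reader might infer that the CMV category is already short by a fifth or more of its cases; the coding of the five cases is not given, and viraemia, infection and test positive are listed, so the shortfall may be zero. A reader might also infer that the undercount grows with dose; the documents hold no data on multi-lineage events by dose level.

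This is a minor improvement to descriptive safety summaries. It touches no efficacy result and no hypothesis test, since none is planned.

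**What to change.** 1. In SAP Appendix B, add the reactivation terms to the CMV and EBV lists.
2. Add the multi-lineage cytopenia terms (pancytopenia, bicytopenia, cytopenia) and state which hematology categories each counts in. One workable rule is to count pancytopenia in all three and assign the others by the affected blood lines; a separate multi-lineage category is an alternative. If the MedDRA version in use lacks any of these terms, the added rows do nothing.
3. Before database lock, compare all coded terms in the blood, investigations and infections classes with the lists, and document any addition.
4. Reconcile SAP 9.2.3 with Appendix A: either list the clinically notable tables, or state in 9.2.3 that they were dropped because of early termination. If they were dropped, items 1 to 3 are not needed for this report.

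The cost is a few rows in an appendix and one short term review, with no new data. Reported category incidences may come out slightly higher.
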